## 12.2.2        Immediately Reportable Events

IREs are events that must be reported immediately to MacroGenics within 24 hours of the study site's awareness of the event.

- All SAEs including any suspected transmission of an infectious agent via a medicinal product

- Pregnancy in a study participant or partner of a study participant
- $\geq$  Grade 3 infusion-related reactions or CRS
- Abnormal liver enzymes that meet the criteria for potential Hy's Law, which is defined as AST and/or ALT that is greater than  $3 \times$  ULN and total bilirubin that is greater than  $2 \times$  ULN and without any alternate etiology
- Immune-related AE of Grade 2 or greater; irAEs are defined in [Section 7.2](#).
- SJS or TEN
- Ocular toxicity
  - $\geq$  Grade 3 keratoconjunctivitis sicca (dry eye)
  - $\geq$  Grade 3 conjunctivitis
  - $\geq$  Grade 3 keratitis
- Administration of a dose significantly greater (specifically, + 20% or higher) than the planned dose, and results in an event of clinical consequence
- AEs leading to permanent discontinuation of study drug in an individual participant
- Discontinuation of the participant from study drug administration for any reason other than disease progression
- Product quality issues with an associated clinical consequence
- Pleural effusion
- Pericardial effusion
- Confirmed or presumed COVID-19/SARS-CoV-2 infection

In those cases, in which the IRE is considered related to study drug, the study drug may be discontinued, and the participant will continue participation in the study for observational safety and efficacy analysis (except for cases where the participant is withdrawn from the study by the investigator or withdrew the consent).

### **12.2.3        Serious Adverse Events**

All SAEs occurring during the study must be reported to the sponsor.

After 30 days following the last dose of study drug administration, if an investigator becomes aware of an SAE that s/he suspects is related to study drug, the investigator should report the event to the sponsor.

Within 24 hours of becoming aware of an SAE, the investigator should provide a completed SAE Report form, via email or fax, to the sponsor. Upon receipt of follow-up information pertaining to an SAE, a follow-up SAE Report form should be submitted to the sponsor within 24 hours of becoming aware of the follow-up information. All SAEs should be entered into the eCRFs within 5 calendar days of the site's awareness.

All Grade 3 or Grade 4 SAEs considered related to study drug must be followed until recovery to baseline or Grade 1.

The investigator must follow all SAEs until resolution and record the date of resolution. Resolution of an event is defined as the return to pre-treatment status or stabilization of the condition with the expectation that it will remain chronic.

All SAEs that have not resolved by the end of the study, or that have not resolved upon discontinuation of the participant's participation in the study, must be followed until any of the following occurs:

- The event resolves
- The event stabilizes
- The event returns to baseline, if a baseline value/status is available
- The event can be attributed to etiology other than the study drug or to factors unrelated to study conduct
- It becomes unlikely that any additional information can be obtained (participant or health care practitioner refusal to provide additional information, lost to follow-up after demonstration of due diligence with follow-up efforts)

Any event requiring hospitalization (or prolongation of hospitalization) that occurs during the course of a participant's participation in a study must be reported as a SAE, except hospitalizations for the following:

- A standard hospitalization for administration of study drug therapy will not be reported as an SAE
- A procedure for protocol/disease-related investigations (e.g., surgery, scans, endoscopy, sampling for laboratory tests, bone marrow sampling, pharmacokinetic or biomarker blood sampling)
- Hospitalizations not intended to treat an acute illness or adverse event (e.g., social reasons such as pending placement in long-term care or hospice facility)
- Surgery or procedure planned before entry into the study (must be documented in the eCRF)

Adverse events related to disease progression should not be recorded as an AE or SAE term, as they will be collected as efficacy endpoints. However, if an AE or SAE occurs in a participant and it is unclear if the event is due to progressive disease, the AE or SAE should be reported.

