## **12 ADVERSE EVENT REPORTING AND ASSESSMENT OF SAFETY**

The safety assessment will be based on the evaluation of AEs that occur from the time of initiation of administration of study drug through 30 days following the last dose of study drug or until the start of a subsequent systemic anticancer therapy (whichever occurs first) and will be determined based on signs, symptoms, physical examination findings, procedure findings, and/or laboratory test results from enrolled participants, as appropriate.

Protocol-related AEs and SAEs will be collected from the time the participant has consented to study participation. AEs and SAEs reported between the time the participant signs the informed consent form (ICF) and the administration of the first dose of study drug will be captured as medical history unless the events are attributed to protocol-specified procedures that are not part of standard of care that occur during this time period, in which case the events will be collected on the Adverse Event CRFs.

SAEs considered related to study drug may be reported at any time, even after the participant's final visit.

Progression of the underlying tumor resulting in hospitalization or death (e.g., participant hospitalized for or dies from progressive disease [PD] only, without any other SAE) will be documented as a tumor response outcome and not as an SAE. If an SAE occurs in a participant and it is unclear whether the event is related to PD, the SAE should be reported.

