## 12.2 Adverse Event Collection and Documentation

### 12.2.1 All Adverse Events

All participants who receive at least one dose of study drug will be considered evaluable for safety. AEs will be determined based on signs, symptoms, physical examination findings, and/or laboratory test results from enrolled participants as appropriate.

All adverse events whether serious or non-serious, will be reported from the time a signed and dated ICF is obtained through 30 days following the last dose of study drug or until the start of a subsequent systemic anticancer therapy (whichever occurs first).

Both protocol-related AEs and SAEs will be collected from the time the participant has consented to study participation. AEs and SAEs reported between the time the participant signs the ICF and the administration of the first dose of study drug will be captured as concurrent medical history unless the events are attributed to protocol-specified procedures. Events attributed to protocol-specified procedures will be collected on the Adverse Event eCRFs and SAE Report form as appropriate.

All adverse events, regardless of seriousness, severity, or presumed relationship to study drug, must be recorded using medical terminology in the source document and the eCRF. All records will need to capture:

- the details of the duration, severity, and seriousness of each adverse event
- the action taken with respect to the study drug(s)
- the investigator's attribution/causality assessment concerning the relationship of the adverse event to study therapy
- the outcome of the event

Whenever possible, diagnoses should be given when signs and symptoms are due to a common etiology (e.g. cough, runny nose, sneezing, sore throat, and head congestion should be reported as "upper respiratory infection"). All treatment measures that are required for AE management must be recorded in the source document. The intensity (severity) of AEs will be assessed using NCI CTCAE v4.03 and serious events will be determined by the definition provided in **Section 12.1.5** above. Generally, all non-serious AEs should be entered into the eCRFs within 10 calendar days of the site's awareness.

**Clinical Laboratory Changes:** Safety laboratory assessments will be evaluated by the investigator to ensure participant safety. Laboratory tests will be graded according to NCI CTCAE v4.03. The investigator is responsible for reviewing the results of all laboratory tests as they become available:

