## 12.2.4 Protocol-Specific Adverse Events of Special Interest

Specific adverse events or groups of AEs will be followed as part of standard safety monitoring activities by the sponsor. The sponsor must be notified of these events in a timely manner, regardless of seriousness (i.e., serious and non-serious adverse events).

- All IRR or CRS events as defined in [Section 7.1.1](#). Grade 3 IRR or CRS events are also considered an IRE, requiring notification to the sponsor within 24 hours.
- Abnormal liver enzymes that meet the criteria for potential Hy's law, which is defined as AST and/or ALT that is greater than  $3 \times$  ULN and total bilirubin that is greater than  $2 \times$  ULN and without any alternate etiology. This is also considered an IRE, requiring notification to the sponsor within 24 hours.
- Immune-related AE of Grade 2 or greater; irAEs are defined in [Section 7.2](#). This is also considered an IRE, requiring notification to the sponsor within 24 hours.
- Skin toxicity that meets the definition of SJS or TEN.
- Pleural effusion
- Pericardial effusion
- PPE
- Ocular toxicity. This is also considered an IRE, requiring notification of the following to the sponsor within 24 hours:
  - $\geq$  Grade 3 keratoconjunctivitis sicca (dry eye)
  - $\geq$  Grade 3 conjunctivitis
  - $\geq$  Grade 3 keratitis

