## **12.3 Other Assessment of Safety**

### **12.3.1 Symptomatic Skeletal Events**

Symptomatic skeletal events (SSEs) are a clinical trial endpoint to describe skeletal morbidity defined as symptomatic fracture, surgery or radiation to bone, or spinal cord compression. Any of the following events must be recorded in the source document and on the SSE eCRF regardless of relationship to disease progression: symptomatic bone fracture, bone pain requiring surgery, bone pain requiring radiation, and/or spinal cord compression.

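### Section 12.2.3 keeps progression-related adverse events out of AE and SAE terms, more widely than Section 12 and against 12.2.1, and no text says that the IRE/AESI duties prevail

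*Protocol*

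**What the plan says.** Four parts of the protocol bear on whether a progression-related event gets an AE record.

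- **General rule, 12.2.1:** "All adverse events, regardless of seriousness, severity, or presumed relationship to study drug, must be recorded using medical terminology". SAP 5.2.1 likewise counts an event as an AE whether or not it is thought to be drug related, and has no exception for progression.
- **Exemption in Section 12:** it covers progression that leads to hospitalization or death. A participant who "dies from progressive disease [PD] only, without any other SAE) will be documented as a tumor response outcome and not as an SAE". The synopsis has a similar provision.
- **Exemption in 12.2.3:** "Adverse events related to disease progression should not be recorded as an AE or SAE term, as they will be collected as efficacy endpoints". The following sentence limits it: where "it is unclear if the event is due to progressive disease, the AE or SAE should be reported".
- **IRE and AESI duties, 12.2.2, 12.2.4 and 12.2.6:** pleural and pericardial effusion are on both lists with no grade or cause qualifier. IREs go to the sponsor within 24 hours of the site's awareness, and 12.2.6 has them documented in the eCRF. For AESIs, "The sponsor must be notified of these events in a timely manner, regardless of seriousness".

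For skeletal events, 12.3.1 settles the question explicitly: "Any of the following events must be recorded in the source document and on the SSE eCRF regardless of relationship to disease progression".

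**The concern.** Safety and tolerability are the primary objective, the study is open label (Section 6.3), and there is no control arm against which a shortfall in recorded events would show. SAP 6.8.1 builds its safety tables from recorded AEs by MedDRA Preferred Term. An event that is denied an AE term because the investigator judges it to be progression does not reach those tables and leaves no AE record for a later reviewer to re-attribute.

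The protocol already has a place for such an event. Section 12.1.4 lets the investigator record an AE as not related (None or Unlikely) because another cause, such as concomitant disease, explains it. Section 12.2.3 removes the event instead of classifying it, and its stated reason is that the efficacy data will hold it.

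**Working it through.** **1. Scope of the rules.**

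| Place | What is kept out | Kept out of what |
|---|---|---|
| 12.2.1; SAP 5.2.1 | Nothing on grounds of presumed drug relationship | – |
| 12 | Hospitalization or death from progression alone | SAE status |
| 12.2.3 | Any AE related to progression, serious or not | AE and SAE terms |
| 12.2.2, 12.2.4, 12.2.6 | Nothing; effusions are unqualified | – |

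Section 12.2.3 is wider than Section 12 in two ways. It reaches non-serious events although it sits in the SAE section, and it covers events related to progression, not only progression itself. No text ranks it against 12.2.1 or against the IRE and AESI lists.

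**2. Do the efficacy data hold these events?** SAP 5.1.1 to 5.1.5 list response, PFS, DoR, OS, tumor size, rPFS, PSA, SSEs and the BPI-sf. Progression is radiographic. Skeletal events and, in the Module A expansion, pain scores are captured. No endpoint holds the Preferred Term, grade or outcome of, for example, an effusion or dyspnea attributed to progression. Appendix 5 also says that symptomatic deterioration does not describe an objective response. The reason given in 12.2.3 therefore holds for only some of the events that it covers.

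**3. Can one event be read both ways?** Yes. Pericardial and pleural effusion are exclusions at entry (Section 5.2, criteria 9f and 26), and Section 7.6 covers their management on study drug. Yet Appendix 5, 2.3.4, names a growing pleural effusion as an example of unequivocal progression in non-measurable disease.

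**4. Size.** The plan states no AE, SAE or AESI rate and no share attributed to progression, so there is no plan figure to reproduce. If k of n participants have an event and d of them are left out, the reported rate is (k − d)/n, and the shift is d/n, never upward. SAP 6.8.1 counts participants, so a row moves only when the participant has no other recorded event in that row.

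- One participant in a 16-person cohort: 1/16 = 6.25, or 6.3 points.
- One participant in the 80-person Module A expansion: 1/80 = 1.25 points.

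The values of k and the shares below are assumptions for illustration. The intervals are exact (Clopper-Pearson); the same method returns protocol Table 10, for example 4/16 = 25.0% (7.3 to 52.4).

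| Assumed k/n | None left out | 25% left out | 50% left out |
|---|---|---|---|
| 4/16 | 25.0% (7.3–52.4) | 3/16 = 18.8% (4.0–45.6) | 2/16 = 12.5% (1.6–38.3) |
| 8/80 | 10.0% (4.4–18.8) | 6/80 = 7.5% (2.8–15.6) | 4/80 = 5.0% (1.4–12.3) |
| 16/80 | 20.0% (11.9–30.4) | 12/80 = 15.0% (8.0–24.7) | 8/80 = 10.0% (4.4–18.8) |

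**5. Which tables.** The effect falls on the all-cause tables: all AEs, Grade 3 or higher, SAEs, fatal AEs and AESIs. The drug-related tables would not have counted an event classed as not related in any case. What is lost there is the chance to correct a wrong attribution.

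**The case against.** The sponsor can say that keeping progression out of the safety data is deliberate, since the synopsis, Section 12 and 12.2.3 all do it, and that a general rule followed by a specific exception is not a contradiction. Section 12.2.1 speaks of presumed relationship to study drug and does not mention progression. Doubtful cases must be reported. Effusions have a 24-hour duty and eCRF entry, and because they are excluded at baseline, an effusion on study will often be of uncertain origin and so reportable. The CRF completion guidelines mentioned in Section 15.2 are not available here and may settle the matter.

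Much of this stands, and it rules out three stronger readings that a reader might infer:

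- *Progression-related events go entirely unrecorded.* The text bars an AE or SAE term and refers the events to the efficacy data; skeletal events have their own form.
- *Effusions are the most exposed events.* Their unqualified IRE and AESI duties protect them better than ordinary AEs. They remain exposed only because those duties are not placed above 12.2.3.
- *The rates are understated.* No document gives a rate or an attribution share, and the bias is zero if no event is left out.

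What does not stand is the claim that the exemptions agree. Their breadth differs, and the clause on unclear cases does nothing for an attribution that is confident and wrong.

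**Conclusion.** The conflict is real and should be resolved. Section 12.2.3 is wider than Section 12, is at odds with 12.2.1 and SAP 5.2.1, and rests on a reason that the efficacy endpoints only partly support. The exposure is limited to events that the investigator confidently attributes to progression. For these, the all-cause safety rates can be biased downward by an amount that the documents do not allow anyone to estimate. The per-participant steps of 6.3 and 1.25 points are arithmetic on the planned cohort sizes, and the larger shifts tabulated above rest wholly on assumed inputs. This merits correction because safety is the primary objective and the change is small. It does not show that any reported rate will be wrong.

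**What to change.** Reconcile the passages in 12.2.3 with wording such as: *The term disease progression, and hospitalization or death due to progression only, are not recorded as an AE or SAE. Signs, symptoms and complications, including every event type listed in 12.2.2 and 12.2.4, are recorded as AEs whether or not they are attributed to progression; where they are, progression is entered as the alternative etiology.* This brings 12.2.3 back to the breadth of Section 12, uses the causality categories already in 12.1.4, and follows the principle that 12.3.1 applies to SSEs on their own eCRF. The CRF completion guidelines should say the same. The tables in SAP 6.8.1 need no change.

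The cost is a sentence or two in the protocol, a line in the guidelines, a few more AE records and slightly higher all-cause AE rates. Deaths and hospitalizations from progression alone stay out of the SAE data, as Section 12 intends.

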## 12.2.4 Protocol-Specific Adverse Events of Special Interest

Specific adverse events or groups of AEs will be followed as part of standard safety monitoring activities by the sponsor. The sponsor must be notified of these events in a timely manner, regardless of seriousness (i.e., serious and non-serious adverse events).

- All IRR or CRS events as defined in [Section 7.1.1](#). Grade 3 IRR or CRS events are also considered an IRE, requiring notification to the sponsor within 24 hours.
- Abnormal liver enzymes that meet the criteria for potential Hy's law, which is defined as AST and/or ALT that is greater than  $3 \times$  ULN and total bilirubin that is greater than  $2 \times$  ULN and without any alternate etiology. This is also considered an IRE, requiring notification to the sponsor within 24 hours.
- Immune-related AE of Grade 2 or greater; irAEs are defined in [Section 7.2](#). This is also considered an IRE, requiring notification to the sponsor within 24 hours.
- Skin toxicity that meets the definition of SJS or TEN.
- Pleural effusion
- Pericardial effusion
- PPE
- Ocular toxicity. This is also considered an IRE, requiring notification of the following to the sponsor within 24 hours:
  - $\geq$  Grade 3 keratoconjunctivitis sicca (dry eye)
  - $\geq$  Grade 3 conjunctivitis
  - $\geq$  Grade 3 keratitis

## 12.2.5 Pregnancy

All reports of pregnancy in female participants or partners of male participants must be reported to the sponsor by study-site personnel within 24 hours of their knowledge of the event using the Pregnancy Exposure Form. Abnormal pregnancy outcomes (e.g., spontaneous abortion, fetal death, stillbirth, congenital anomalies, ectopic pregnancy) are considered SAEs and must be reported using the SAE Report form. Any participant who becomes pregnant during the study must discontinue further study drug administration.

Because the effect of the study drug on sperm is unknown, pregnancies in partners of male participants included in the study will be reported by the study-site personnel within 24 hours of their knowledge of the event. If the female partner of a male participant becomes pregnant, the partner must be requested to complete a Pregnant Partner Consent Form so that pregnant partner, fetal, and/or newborn information can be collected.

Upon confirmation of serum or urine pregnancy testing, the participant will be followed for the outcome of pregnancy. Follow-up information will be collected for all live newborns at

birth and 6 months after the birth. All necessary information will be collected to assess the effects of study drug on the newborn. If necessary, the follow-up period will be extended for the newborn.

## 12.2.6 Reporting of Adverse Events to the Sponsor

Throughout the study, the investigator must document all AEs, SAEs, and other IREs, as defined in [Section 12.2.2](#) in the eCRFs in a timely manner. See **Table 9**, Safety Reporting by Event Type, for details.

The investigator must immediately complete and transmit the SAE Report Form, within 24 hours of identifying the event, to MacroGenics Product Safety or designee. The SAE Report form and Completion Guidelines, and Contact Information for Reporting SAEs, are provided by the sponsor.

For reports of pregnancy, the MacroGenics Pregnancy Exposure Form must be completed and transmitted. The investigator must attempt to follow the pregnancy to term or termination in order to report the outcome and health status of the mother and child. The Pregnancy Exposure Form is provided by the sponsor.

Please refer to the **Table 9** for reporting timeframes to MacroGenics by event type.

**Table 9** Safety Reporting by Event Type

| Type of Event:                                           | Hard Copy Form/Timeline for reporting/Where to Report                                       | eCRF Timeline for Data Entry         |
|----------------------------------------------------------|---------------------------------------------------------------------------------------------|--------------------------------------|
| Serious Adverse Event (SAE)                              | Serious Adverse Event Form within 24 hours of awareness
Report Email to

Or fax to | Within 5 calendar days of awareness  |
| Pregnancy                                                | Pregnancy Exposure Form/
Within 24 hours of awareness/
Email to

Or fax to      | Within 5 calendar days of awareness  |
| Other IREs, as defined in Section 12.2.2 | Not Applicable                                                                              | Within 24 hours of awareness         |
| Non-Serious Adverse Events (except for Pregnancy):       | Not Applicable                                                                              | Within 10 calendar days of awareness |

Abbreviations: eCRF = electronic case report form; IRE = immediately reportable event; SAE = serious adverse event.

## **12.3 Other Assessment of Safety**

### **12.3.1 Symptomatic Skeletal Events**

Symptomatic skeletal events (SSEs) are a clinical trial endpoint to describe skeletal morbidity defined as symptomatic fracture, surgery or radiation to bone, or spinal cord compression. Any of the following events must be recorded in the source document and on the SSE eCRF regardless of relationship to disease progression: symptomatic bone fracture, bone pain requiring surgery, bone pain requiring radiation, and/or spinal cord compression.

